Efficacy of near-assisted learning (NAL) in improving students' OSCE grades: A single-blinded RCT

Document date: 10/4/2019

Study protocol:

In this single-blinded randomized controlled trial, 1st year male medical students of Sulaiman Alrajhi Colleges were invited via emails to participate voluntarily. Forty-eight students agreed to join and, after informed consent, were randomly assigned to one of two groups; the near-assisted learning group (The intervention) and the self-directed learning group (The control arm). Meanwhile, a group of 5th year medical students, known to be the top in their class, were invited to participate as instructors during the OSCE sessions. After their acceptance, they underwent extensive 2-week crash course focusing in basics of medical education, teaching and feedback cycle, along with quick supervised revision of systemic and general physical examination. At the analysis phase, scores of the previous batch were also included as a 3rd group for comparison. The study was concluded after 9 days, when the students had their skills evaluated during OSCE examination.

Analysis plan:

Through SPSS 23rd edition, frequency, proportion analysis, chi-square and Fisher's exact test were used. A probability value of less than .05 was determined for significance.

Results:

Those scoring B or better in the near-assisted learning, self-directed learning and the students of the previous batch groups were 22 (88%), 19 (82.6%) and 7 (50%), respectively ($p= 0.025$). More participants from the last group score A or more in comparison to the other two groups. On the other hand, less students failed the OSCE exam from the near-assisted and self-directed learning groups than the group of the prior batch.

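### The only p-value (0.025) comes from a three-group test that includes a non-randomised earlier batch; the randomised comparison of NAL with self-directed learning is never reported, and for grade B or better it is inconclusive (Fisher p = 0.70)

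*Combined protocol and SAP*

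**What the plan says.** The title presents the study as a test of efficacy: "Efficacy of near-assisted learning (NAL) in improving students' OSCE grades: A single-blinded RCT". Under Study protocol, the 48 consenting students "were randomly assigned to one of two groups", with NAL labelled the intervention and SDL the control arm. The same paragraph adds: "At the analysis phase, scores of the previous batch were also included as a 3rd group for comparison".

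The Analysis plan lists methods, "frequency, proportion analysis, chi-square and Fisher's exact test were used", and a threshold, "A probability value of less than .05 was determined for significance". It does not say which groups are compared or which comparison is primary.

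The Results give grade B or better for NAL, SDL and the earlier batch, in that order, as "22 (88%), 19 (82.6%) and 7 (50%), respectively ($p= 0.025". Two further statements carry no counts and no test: "More participants from the last group score A or more in comparison to the other two groups" and "less students failed the OSCE exam from the near-assisted and self-directed learning groups than the group of the prior batch". If the last group means the earlier batch, as the listed order suggests, both statements set the two arms against that batch. No p-value, difference or confidence interval is given for NAL against SDL at any cut-off.

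**The concern.** Randomisation protects one comparison here, NAL against SDL. The earlier batch sat its examination as a different cohort and was brought in only for analysis, so any difference from it may reflect the students, the examination or the marking as well as the teaching.

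A three-group test can be significant because of that batch alone. Because 0.025 is the only inferential result in a document titled as an efficacy trial, a reader may take it as evidence that NAL works, while the question the trial was built to answer goes unreported.

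**Working it through.** **Inputs.** Counts and percentages from the Results: 22 (88%), 19 (82.6%), 7 (50%). Number randomised from Study protocol: 48. Threshold from the Analysis plan: .05; two-sided testing is assumed because the plan does not say.

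**1. Group sizes (derived, not stated).** Each size is the only whole number that gives the stated percentage: 22/25 = 88%, 19/23 = 82.6%, 7/14 = 50%. As a check, 25 + 23 = 48, the number randomised.

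**2. Reproducing 0.025.** The table of B or better against below B is 22/3 (NAL), 19/4 (SDL), 7/7 (earlier batch).

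- Fisher-Freeman-Halton exact test (sum of the probabilities of all tables with the same margins that are no more likely than the observed one): p = 0.0254.
- Pearson chi-square, 2 df: 7.976, p = 0.0185.
- Likelihood-ratio chi-square, 2 df: 7.228, p = 0.0269.

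Of these, only the exact three-group test rounds to 0.025. The smallest expected count is 14 × 14/62 = 3.16, so an exact test is a natural choice.

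**3. The randomised comparison.**

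- Difference: 0.880 − 0.826 = +0.054, or +5.4 points.
- Wilson 95% limits: NAL 0.700 to 0.958; SDL 0.629 to 0.930.
- Newcombe lower limit: 0.054 − √[(0.880 − 0.700)² + (0.930 − 0.826)²] = −0.154.
- Newcombe upper limit: 0.054 + √[(0.958 − 0.880)² + (0.826 − 0.629)²] = +0.266.
- Two-sided Fisher p = 0.696; uncorrected Pearson p = 0.597. Sample odds ratio (22 × 4)/(3 × 19) = 1.54.

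**4. Where the three-group signal lies.** The likelihood-ratio statistic, G = 2Σ O ln(O/E), splits exactly into two parts:

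| Comparison | G | Share |
|---|---|---|
| NAL 22/25 vs SDL 19/23 | 0.28 | 4% |
| Both arms 41/48 vs earlier batch 7/14 | 6.95 | 96% |
| Three groups | 7.23 | 100% |

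Fisher's test of 41/48 against 7/14 gives p = 0.010.

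**5. Would 0.025 have changed if NAL had done worse?** Hold the totals at 41/48 randomised and 7/14 earlier batch, and redistribute the 41 successes between the arms in all eight possible ways:

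| NAL /25 | SDL /23 | Three-group exact p |
|---|---|---|
| 18 | 23 | 0.0006 |
| 19 | 22 | 0.0044 |
| 20 | 21 | 0.0173 |
| 21 | 20 | 0.0306 |
| 22 (observed) | 19 | 0.0254 |
| 23 | 18 | 0.0129 |
| 24 | 17 | 0.0024 |
| 25 | 16 | 0.0002 |

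Every split falls below .05. Two rows matter most. At 21/25 vs 20/23 (84.0% vs 87.0%) the arms are nearly equal and the two-arm Fisher p is 1.00. At 20/25 vs 21/23 (80.0% vs 91.3%) NAL does worse, with a two-arm p of 0.42.

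**6. Illustration under assumed rates.** Suppose NAL and SDL share a true rate of 41/48 = 85.4%. Full enumeration of the 25/23/14 exact test at p < .05 gives rejection rates of 65%, 41%, 20%, 7% and 4.5% when the earlier batch's true rate is 50%, 60%, 70%, 80% and 85.4%. That rate is unknown, so this is a range and not a finding. It shows that with no effect of NAL over SDL, the chance of a significant result depends on the earlier batch.

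**The case against.** The document makes no false claim. It never says that 0.025 shows NAL beating SDL, it discloses that the earlier batch was added for analysis, and it attaches the p-value openly to all three proportions. That is fair: the defect is an omitted comparison and a result open to misreading, not a wrong number. Disclosure still does not supply the missing randomised contrast.

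A second objection is that no two-sided p-value gives direction, and that the three-group p does respond to a large gap between the arms. This also stands in part. In three of the eight splits (18/23, 24/17 and 25/16) the two-arm Fisher test is itself below .05. The argument rests on the near-equal and NAL-worse splits, where the three-group p is significant and the two-arm test is not.

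A third is that the trial is too small for the two-arm test to be useful. Power is indeed low: by full enumeration, Fisher's test has 6.5% at the observed rates and 49% for an assumed 95% against 75%. That is a reason to show the interval and call the result inconclusive, not to leave the comparison out.

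Finally, the two-arm test could be called post hoc. The contrast follows from the design, which names an intervention and a control arm, but the Analysis plan does not name it. The report should say both.

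**Conclusion.** The concern holds. The trial's only p-value does not test its randomised question and is driven almost wholly by a non-randomised group. For B or better, NAL against SDL is +5.4 points, 95% CI -15.4 to +26.6, Fisher p = 0.70: compatible with a sizeable benefit or a sizeable harm, so inconclusive. It must not be read as showing that the arms are equal.

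This rests on the derived group sizes, which are unique and sum correctly, and on two-sided testing; the one-sided Fisher p is 0.45, so sidedness does not change the conclusion. That 0.025 came from the exact three-group test is inferred from the numerical match. The cut-offs for A or more and for failing cannot be checked without counts.

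**What to change.** 1. In the Analysis plan and Results, make NAL against SDL in the 48 randomised students the efficacy comparison. For B or better report 22/25 vs 19/23, the difference with its 95% CI and the Fisher p-value, described as inconclusive.
2. State that this comparison follows from the two-arm randomised design, was not prespecified in the plan, and was designated after the results were known.
3. Give counts and the same two-arm contrast for A or more and for failing. Since the plan ranks no outcome, show all three cut-offs together and say that the p-values are not adjusted for multiplicity.
4. Keep 0.025 only as a secondary, non-randomised three-group comparison. Name the test and group sizes, and say that it is not evidence of NAL's efficacy.

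The cost is rewording plus 2×2 analyses of data already held. The headline result becomes non-significant, which is what the randomised data for B or better support.

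### No OSCE grade cut is fixed in the Analysis plan; the Results use three, quantify only B or better, and the direction against the previous batch changes with the cut

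*Combined protocol and SAP*

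**What the plan says.** The Analysis plan is two sentences long. It says that "frequency, proportion analysis, chi-square and Fisher's exact test were used" and that "A probability value of less than .05 was determined for significance". It names no primary outcome, no grade that defines success, and no way of handling more than one cut of the same grade.

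The Results use three cuts:

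- **B or better:** near-assisted learning (NAL), self-directed learning and the previous batch "were 22 (88%), 19 (82.6%) and 7 (50%), respectively ($p= 0.025".
- **A or more:** "More participants from the last group score A or more in comparison to the other two groups". There is no count, percentage or p-value. The group listed last in the preceding sentence is the previous batch.
- **Fail:** "less students failed the OSCE exam from the near-assisted and self-directed learning groups than the group of the prior batch". Again there are no numbers.

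The Study protocol says that "Forty-eight students agreed to join and, after informed consent, were randomly assigned to one of two groups". The previous batch was not randomised and was added as a third group at the analysis phase.

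**The concern.** The title asks whether NAL improves OSCE grades. A graded outcome can be cut in several places, and if the cut is not fixed in advance, a p-value at one cut is hard to interpret. Here the only p-value sits at a cut that favours the trial arms, while another cut of the same grade favours the previous batch and has no numbers.

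A uniform upward shift in grades would not reverse at the top. The reported directions suggest instead that the previous batch had more students at both ends of the scale. A reader who sees only the 0.025 would miss this and could take B or better as evidence of a general improvement. The trial's own contrast, NAL against self-directed learning, is not reported at A or more or at fail.

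**Working it through.** **1. Group sizes** (implied by the Results, not stated per group). 22/0.88 = 25; 19/0.826 = 23; 7/0.50 = 14. The two trial arms give 25 + 23 = 48, which matches the number randomised. The total is 62.

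**2. The stated p-value.** Table (B or better, below B): 22, 3; 19, 4; 7, 7.
- Fisher-Freeman-Halton exact test: p = 0.0254, which reproduces 0.025.
- Pearson chi-square: 7.98 on 2 df, p = 0.0185.

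The stated figure is therefore a three-group exact test that includes the previous batch.

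**3. The randomised comparison at B or better.** 22/25 − 19/23 = 88.0% − 82.6% = 5.4 percentage points; Newcombe 95% CI about −15 to +27; Fisher p = 0.70. By contrast, both trial arms pooled (41/48) against the previous batch (7/14) give Fisher p = 0.010. The significant result comes from the non-randomised group.

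**4. Bounds at A or more.** Only 7 of 14 in the previous batch reached B or better, so at most 7 of 14 reached A or more.
- If the comparison is of counts, each trial arm has at most 6: at most 6/25 (24%) and 6/23 (26%). Then at least 22 − 6 = 16 NAL students and 19 − 6 = 13 self-directed students counted at B or better were below A.
- If it is of percentages, each arm is below 50%: at most 12/25 and 11/23.

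**5. What the reversal could be worth.** The real counts are not given. The cases below are assumptions that fit the text, tested with the same three-group exact test as in step 2.

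| NAL (of 25) | Self-directed (of 23) | Previous batch (of 14) | Exact p |
|---|---|---|---|
| 0 | 0 | 7 | < 0.001 |
| 3 | 3 | 7 | 0.019 |
| 6 | 6 | 7 | 0.24 |
| 5 | 5 | 6 | 0.28 |
| 3 | 3 | 4 | 0.41 |
| 12 | 11 | 7 | about 1 (percentage reading only) |

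The text is compatible with a clearly significant reversal and with a trivial one.

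**6. Fail.** No counts are given, so nothing can be computed beyond the stated direction.

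**The case against.** The strongest reply is that nothing adverse was hidden. The Results state the direction at A or more openly and set it against the failures. Fail also favours the trial arms and also lacks numbers, so two of the three cuts point the same way and the missing figures do not follow the direction of the result. This stands. A reader might infer that an unfavourable cut was suppressed, or that only the favourable cut was tested; the text shows only what was reported.

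Second, a reader might infer that the trial's conclusion about NAL flips with the cut. The document states no formal conclusion. The reversal is one of direction only, and only against the previous batch. Nothing shows a reversal between NAL and self-directed learning, and at the one quantified cut that contrast is already null. This also stands.

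Third, one might apply Bonferroni over three cuts: 3 × 0.0254 = 0.076, or a threshold of 0.05/3 = 0.0167, so 0.025 would fail. The plan defines no such family, and the cuts are nested and correlated, so the correction is conservative and debatable. One primary cut or one ordinal analysis would need none. The point does not rest on this figure.

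Fourth, an illustration such as 3/25, 3/23 and 7/14 is an extreme case: it assumes that every previous-batch student at B or better also reached A. Its Pearson p of 0.010 should not be set against the exact 0.025; like for like it is 0.019, and other compatible counts give 0.24 to 0.41. It shows what is possible, not what happened.

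Finally, the grading scale is not given, so other grades may lie between B and A.

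What the reply does not answer is that no cut is fixed in the plan, two of the three cuts have no numbers, and the arms are not compared with each other at those two.

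**Conclusion.** The point holds as a gap in specification and reporting. The document shows no cut fixed in advance, and the only p-value, 0.025, belongs to one of three cuts in use. Against the previous batch, B or better and fail favour the trial arms, while A or more favours the previous batch. The size of that reversal is unknown, beyond the limit of 7/14 in the previous batch. For the randomised question, the only available result is 5.4 points at B or better (95% CI about −15 to +27, p = 0.70), which is no evidence of a difference but does not exclude a sizeable one either way.

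This rests on two readings: that the group sizes implied by the percentages are right (they sum to 48 and reproduce the p-value), and that the last group is the previous batch (the order of the list and the contrast that follows support this). A cut may have been fixed in a record outside this document; if so, saying so would settle that part. It does not follow that a result was withheld, or that NAL did worse than self-directed learning at any cut.

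**What to change.** - **Results:** give n (%) in every grade, and at A or more, B or better and fail, for each of the three groups. Replace the two sentences that give a direction without numbers.
- **Randomised comparison:** report the NAL minus self-directed difference with a 95% CI at each cut, or one ordinal comparison of the full grade between these two arms. Keep this separate from any comparison with the previous batch.
- **Analysis plan:** state that no cut is shown as fixed in advance, or cite the dated record if one exists. Without such a record, label the 0.025 as exploratory.
- **Interpretation:** state that the direction against the previous batch reverses at A or more, and do not base a claim of improved grades on B or better alone.

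Repeating the three-group test at every cut is not recommended, because it does not address the trial's question.

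The cost is one extra table, assuming the grades behind the reported results are still held, and some rewording. No new data are needed. The downside is a less favourable headline.
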